- 6) Facial palsy affects how I feel about myself (self-esteem) (**ITG = Facial palsy: building your self-esteem**)

Participants are invited to rate each statement according to how frequently they experience each difficulty. There are 5 options: all the time; a lot of the time; only occasionally; never or N/A. Participants are eligible to complete ITGs if they have rated having difficulties relating to the topic of the ITG 'all the time' or 'a lot of the time'. Participants will also be asked to rank the six statements in order of how much of a concern they are for them (1 = most important concern, 6 = least important concern). If participants are eligible to complete multiple ITGs (i.e. they rate experiencing difficulties 'all the time' or 'a lot of the time' for multiple topics), then they will complete ITGs in order of how much of a concern that area is for the participant. . They will be informed that they may be able to complete the next ITG that they are eligible for, at the completion of the 4-6 week trial period for their initial ITG.

At the completion of the 4-6 week trial period, participants will be invited to re-complete the original screening questionnaire and, if eligible (e.g. they still experience difficulties on one of the remaining topics 'all the time' or 'a lot of the time'), will be invited to trial the next ITG. If they do not wish to complete further ITGs then the participant will be thanked for their involvement in the study and their involvement will be registered as 'complete'

Participants who do not meet eligibility criteria will be thanked for their interest in the study and signposted to the Facial Palsy UK website for general information and advice for how to best manage facial palsy:

Thank you for your interest in this study. Unfortunately you do not currently meet the inclusion criteria for this study. For further information and advice about managing facial palsy please visit facialpalsy.org.uk or contact your NHS facial palsy service.

The screening questionnaires will also ask potential participants to provide information about their (or their family member or relative's) facial palsy diagnosis/type and date of onset.

7.3. Informed Consent

Participants must personally sign and date the latest approved version of the Informed Consent form before any study specific procedures are performed. As permitted by 'eIDAS' Regulation (EU) Number 910/2014 framework for electronic signatures, this will be typewritten in Survey Hero (i.e. participants will type their name and select the day's date to confirm consent).

The consent process will be identical for participants who are individuals with facial palsy and participants who are friends or relatives of someone with facial palsy.

Written versions of the Participant Information Sheet (physical copy to patients recruited from the Oxford Facial Palsy Service and pdf copy sent via email to participants recruited from Facial Palsy UK) and Informed Consent (presented on Survey Hero) will be presented to the participants detailing no less than: the exact nature of the study; what it will involve for the participant; the implications and constraints of the protocol; the known side effects and any risks involved in taking part. It will be clearly stated that the participant is free to withdraw from the study at any time for any reason without prejudice to future care, without affecting their legal rights, and with no obligation to give the reason for withdrawal.

The participant will be allowed as much time as wished to consider the information, and the opportunity to question the Investigator, their GP or other independent parties to decide whether they will participate in the study. Written Informed Consent will then be obtained by means of participant dated signature and dated signature of the person who presented and obtained the Informed Consent. The person who obtained the consent must be suitably qualified and experienced, and have been authorised to do so by the Chief/Principal Investigator.

The electronic copy of the signed Informed Consent will be exported to PDF, printed, signed and dated by the Principal investigator and then scanned/mailed to the participant. The original signed form will be retained at the study site.

For participants recruited in OUH clinics a copy of the signed consent form will also go in the medical notes.

7.4. Baseline Assessments

The following questionnaires will be administered via Survey Hero once participants have read the information sheet and met eligibility criteria. This will be completed online remotely for participants recruited via Facial Palsy UK (social media, website and mailing list) and online on a laptop during clinic for participants attending the Oxford Facial Palsy Service clinic (or remotely via Survey Hero if this is their preference).

Primary Objective

To evaluate the effectiveness of Information and Therapy guides at improving the psychosocial wellbeing of people with a diagnosis of facial palsy

This will be assessed by the change in an individual's self-report questionnaires before and after a four-to-six week intervention, using one of six information and therapy guides (the guide that they are given will be determined by their responses on a screening questionnaire). The questionnaires used will be:

Hospital Anxiety and Depression Scale (15): A 14-item scale with two seven-item subscales looking at anxiety and depression. A score equal-to-or-lower-than 7 on a subscale falls below the clinical cut-off, a score of 8-10 indicates probably clinically significant anxiety or depression, while a score of 11 or more indicates clinically significant anxiety or depression. It is well validated in the physical health population, excluding somatic symptoms of anxiety and depression that may overlap with symptoms of a physical health condition (15). It has been shown to have good test-retest reliability (= .70 to .84; 16).

FACE-Q Satisfaction with appearance (17): A nine-item scale assessing an individual's concerns regarding their facial appearance. The higher the score, the greater the patient's dissatisfaction with their appearance, with a highest possible score being 32. This measure has been demonstrated to have good reliability within a plastic surgery population (17).

FACE-Q Psychological function (18): This 11-item scale measures psychological wellbeing using a series of positively worded statements, with participants invited to rate how much they agree/disagree with each statement. A high score (maximum = 40) indicates greater psychological wellbeing. This measure has been validated within a clinical setting and has been shown to have a Cronbach alpha of .96, indicating very good internal consistency (18).

FACE-Q Social functioning (18): Like the FACE-Q psychological function scale, participants are provided with a series of positively worded statements. In this scale there are 9 statements and they pertain to measuring social functioning. Just as with the psychological function scale, the social functioning scale has a Cronbach alpha of .96 and has been shown to have good convergent and discriminant construct validity.

Facial Disability Index (19): A 10-item self-report measure of physical and social function in people with facial palsy. Both the physical (=.88) and social (=.83) subscales have been shown to have good internal consistency and construct validity (19). Each scale is scored out of 100 (100 = high function).

This measure of facial function will allow the researchers to control for improvement or decline in facial palsy symptoms when assessing the impact of the ITG's on psychological wellbeing.

Note: the friends/relatives of participants with facial palsy are not required to complete questionnaires, unless they themselves are actively participating in the study (i.e. are trialling the family, friend or partner ITG)

Secondary Objectives

To evaluate the effectiveness of Information and Therapy guides at improving the psychosocial welling of friends and relatives of people with a diagnosis of facial palsy

This will be assessed by the change in friend's/relative's self-report questionnaires before and after a four-to-six week intervention using the information and therapy guide: Facial palsy: Advice for friends, relatives and partners of people with facial palsy.

The outcome measures used will be the **Hospital Anxiety and Depression Scale** (described above), along with the **Adult Carer Quality of Life Questionnaire** (20). This is a 40-item self-report scale that measures the overall quality of life for adult carers. Subscale scores include: support for caring; caring choice; caring stress; money matters; personal growth; sense of value; ability to care and carer satisfaction. Scores fall on a 0-120 scale, with higher scores indicating better quality of life.

7.5. Subsequent Visits

Participants will be followed up at two different time points:

After 2-3 weeks:

Participants will be contacted via email to remind them to complete their current ITG. They will also be sent a link to an online questionnaire, pertaining to their ratings of acceptability and usability of the ITG (participant satisfaction questionnaire; in line with the **Tertiary Objective**: To evaluate the acceptability and usability of Information and Therapy guides for people with facial palsy and/or their friend or relative).

After 4-6 weeks:

Participants will be contacted via email to thank them for completing their current ITG. They will be sent a link to an online questionnaire, pertaining to their ratings of acceptability and usability of the ITG (participant satisfaction questionnaire; in line with the **Tertiary Objective**: To evaluate the acceptability and usability of Information and Therapy guides for people with facial palsy and/or their friend or relative).

Participants will also be sent a web link to re-complete their baseline assessments (in line with the **Primary and Secondary Objectives**).

Finally, participants with facial palsy will be invited to re-complete the initial ITG screening questionnaire, to determine whether they might be eligible to complete a further ITG. If eligible, consent will be sought again and the above process will repeat (up to a maximum of 6 times, once for each ITG). Since participants who are friends/relatives of people with facial palsy will only have one ITG available to them, they will not be provided with the opportunity to complete a further ITG.

7.6. Discontinuation/Withdrawal of Participants from Study

Each participant has the right to withdraw from the study at any time. In addition, the Investigator may discontinue a participant from the study at any time if the Investigator considers it necessary for any reason including:

- Ineligibility (either arising during the study or retrospectively having been overlooked at screening)
- Significant protocol deviation
- Withdrawal of Consent (withdrawn participants will be replaced and their data will be excluded from analysis)

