At the end of the four-to-six week period, participants will be re-administered the baseline questionnaires (via web-link to Survey Hero), along with a questionnaire designed for the purpose of the current study measuring the participants’ ratings of acceptability and usability of the ITGs (participant satisfaction questionnaire). Participants will have a 2 week window to complete the final questionnaires after they have been sent to them at the end of the ITG trial period. If they do not complete the questionnaires in this window, they will be withdrawn from the study. Participants with facial palsy will also be re-administered the initial screening questionnaire. This will indicate whether the participant is eligible to complete a further ITG. If this is the case, then their post-intervention questionnaires will serve as a new baseline and the participant will be invited to complete the new ITG over a second four-to-six week period (followed by the same follow-up assessments as followed the first ITG). This process will occur up to a maximum of six times (reflecting the potential for a participant to trial all six ITGs). If they do not wish to complete further ITGs then the participant will be thanked for their involvement in the study and their involvement will be registered as ‘complete’. All participants will be provided with a separate email link to complete the relevant questionnaires at each stage (e.g. screening, baseline, 2-3 week satisfaction, 4-6 week final questionnaires). The email will also remind them of their unique ID number, for them to enter at the start of the questionnaires. This will help their responses to be matched with their previous responses.

We aim to trial the ITGs over a period of one year (July 2019 – May 2020). This will lead to the predicted sample sizes of 140 participants (120 with facial palsy, 20 per each of the 6 guides; 20 friends and family). This target is based on there being approximately 3000 people who have access to the Facial Palsy UK website. Given that approximately 1/3 people with facial palsy experience a significant level of distress (5); we hope that our ITGs would be relevant to, and accessible by, around 1000 people. 140 is therefore a conservative estimate of the number of participants that we will be able to recruit. Recruitment and completion will be monitored in case recruitment should be extended.

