9.3. Analysis of Outcome Measures

A pre-post design will be used to determine whether the use of ITGs lead to a significant improvement in the psychosocial wellbeing of people with facial palsy and or their friends and relatives, as measured by the Hospital Anxiety and Depression Scale, Face-Q – Social function (people with facial palsy only), Face-Q – Psychological function (people with facial palsy only), Face-Q – Appearance-related psychosocial distress (people with facial palsy only) and the Facial Disability Index (people with facial palsy only). This change will be measured for each individual ITG, using paired-samples t-tests. The Facial Disability Index can also be used to control for improvement in facial palsy symptoms, when assessing the impact of ITGs on scores on measures of psychological wellbeing. In the instance of a significant change in facial palsy symptoms being observed, separate ANCOVAs will be used, with Facial Disability Index score being used as a covariate and scores on individual measures of psychosocial wellbeing serving as within-subjects factors.

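### Section 7.6 excludes a withdrawn participant's data without limiting this to the guide in progress, so a finished earlier guide can leave the analysis because of a later withdrawal

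*Combined protocol and SAP*

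**What the plan says.** Section 7.6 is framed around leaving the study: "Each participant has the right to withdraw from the study at any time". Its third listed reason for discontinuation carries the data rule: "Withdrawal of Consent (withdrawn participants will be replaced and their data will be excluded from analysis". No words limit this to the guide in use at the time, and nothing is said about guides already finished.

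Elsewhere the protocol works guide by guide:

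- Section 9.3, on the analysis: "This change will be measured for each individual ITG, using paired-samples t-tests". Section 9.1 says the same.
- Section 5, on repeat use: "This process will occur up to a maximum of six times (reflecting the potential for a participant to trial all six ITGs". When a further guide is started, "their post-intervention questionnaires will serve as a new baseline".
- Section 7.5, for a participant eligible for another guide: "consent will be sought again and the above process will repeat".
- Sections 5 and 7.2, for a participant who does not want another guide: the person is "thanked for their involvement in the study and their involvement will be registered as" complete. No rule excludes that person's data.

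Friends and relatives have a single guide (section 7.5).

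**The concern.** The unit of analysis is one pre-post pair for one guide, but the unit of exclusion is the person. The two agree for anyone who uses one guide. They part company once a participant starts a second, because a later withdrawal then reaches back to a pair that was complete and on time.

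Two things are at stake. Usable data on the primary-objective measures, and the satisfaction ratings that go with them, are set aside in a study that plans only 20 per guide. And whether a pair is analysed depends on an event after its outcome was measured. If that event is related to how the person responded to the earlier guide, the estimate for the earlier guide is selected. Replacing the person restores the count but not the make-up of the group. Section 7.3 lets participants withdraw without giving a reason, so the team cannot rely on being able to check whether the loss is related to response.

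**Working it through.** **The plan's own figure.** Section 9.2: 6 guides × 20 + 20 friends and family = 140. This reproduces. No power analysis was done, so there is no power figure to check.

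**The rule applied to two people.** Both finish guide 1 with complete pre and post scores, and both are eligible for guide 2.

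- Person A declines guide 2. Sections 5 and 7.2 register A as complete. Pairs analysed: 1.
- Person B consents to guide 2 and withdraws consent part-way. Under the literal wording of 7.6, B's data are excluded. Pairs analysed: 0.

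In general, withdrawing during guide k leaves 0 pairs, while declining guide k leaves k − 1. That A's pair is kept is inferred from the complete status and the absence of any exclusion rule.

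**Size with at most two guides.** The documents give neither rate needed, so both are assumptions:

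- w = chance of withdrawing consent during a guide, taken as 5%, 10% and 20%.
- c = share of first-guide finishers who start a second guide, taken as 1 (everyone) and 0.25.

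Per person starting a first guide:

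- finished pairs F = (1 − w) + c(1 − w)²
- finished pairs excluded E = c × w × (1 − w)
- share excluded E/F = c × w / [1 + c(1 − w)]

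| w | F (c = 1) | E (c = 1) | Share excluded (c = 1) | Share excluded (c = 0.25) |
|---|---|---|---|---|
| 5% | 1.853 | 0.048 | 2.6% | 0.0125/1.2375 = 1.0% |
| 10% | 1.710 | 0.090 | 5.3% | 0.025/1.225 = 2.0% |
| 20% | 1.440 | 0.160 | 11.1% | 0.05/1.20 = 4.2% |

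The whole loss falls on the first guide, where the share of finished pairs excluded is c × w. Per 20 finished first-guide pairs, that is 1, 2 or 4 pairs at c = 1, and 0.25, 0.5 or 1 pair at c = 0.25. These counts are before replacement. If exclusion applied only to the guide-use in progress, E would be 0 throughout.

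**The case against.** The strongest reply is that the clause is loose rather than wrong. The exclusion is attached to withdrawal of consent, and consent is renewed for each guide, so the consent being withdrawn could naturally be that for the current guide. This stands as a possible intention. But 7.6 speaks of withdrawing from the study and of the participant's data without limit, and an analyst following the text would drop the earlier pair.

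A second reply is that few people will be affected. Section 9.2 plans 120 people with facial palsy for 6 × 20 = 120 guide places, which, if the places are guide-uses, averages one guide each. Participants may decline, or may no longer qualify on re-screening, and both routes keep their data. Withdrawn participants are also replaced. This stands, and it is why the size above is confined to two guides. A reader might extend the sum to six guides: if nobody declined or lost eligibility, withdrawal of 5% to 20% per guide would exclude 12.4% to 46.7% of finished pairs. The arithmetic is right, but the sample plan gives no support for everyone using six guides.

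A third reply is that excluding data when consent is withdrawn protects participants and is a defensible default. That is fair for the guide in progress. It is a weaker argument for a guide already completed under its own consent, provided the participant can still ask for removal.

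**Conclusion.** The point holds in a limited form. As worded, 7.6 makes the inclusion of a finished guide depend on a later event, and treats withdrawing from a further guide differently from declining it. The loss is about 3% to 11% of finished pairs if every first-guide finisher starts a second and goes no further, and about 1% to 4% if a quarter do, at assumed withdrawal of 5% to 20% per guide. It touches only participants with facial palsy who go on to another guide.

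Three stronger inferences are not supported:

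- That earlier results are erased. The text says excluded from analysis, not deleted.
- That the guides will look better than they are. It is plausible that people who gained little withdraw more often, but nothing in the documents links later withdrawal to earlier response, so the direction of any bias is unknown.
- That missing a later guide's questionnaire window also removes earlier guides. Section 5 says of that case: "If they do not complete the questionnaires in this window, they will be withdrawn from the study". The exclusion, however, sits in the withdrawal-of-consent item of 7.6, and whether it reaches these participants is unclear. The point does not rest on it.

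For an uncontrolled pilot this is a modest defect, but one worth settling before analysis.

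**What to change.** Reword the withdrawal-of-consent item in 7.6 per guide-use:

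- Withdrawal of consent during a guide excludes and replaces that guide-use only.
- Pre-post and satisfaction data from guides already completed under their own consent are analysed, unless the participant asks for their removal.
- Where a post-score also served as the baseline of the abandoned guide, it is kept as the post-score of the completed one.
- State whether the exclusion applies to participants withdrawn for missing the questionnaire window and, if so, that it too is limited to that guide-use.

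Align the information sheet and the repeat consent with this. Their text was not available for this review, so they may already cover part of it.

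The cost is a small amendment needing ethics approval (section 12.3) and individual handling of removal requests. No further data collection is needed.

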4. OBJECTIVES AND OUTCOME MEASURES

Objectives	Outcome Measures	Timepoint(s) of evaluation of this outcome measure (if applicable)
Primary Objective To evaluate the effectiveness of Information and Therapy guides at improving the psychosocial wellbeing of people with a diagnosis of facial palsy	Hospital Anxiety and Depression Scale Face-Q – Social function Face-Q – Psychological function Face-Q – Appearance-related psychosocial distress	1) Prior to participant using ITG 2) After participant has used ITG for 4-6

	Facial Disability Index	weeks
Secondary Objectives To evaluate the effectiveness of Information and Therapy guides at improving the psychosocial welling of friends and relatives of people with a diagnosis of facial palsy	Hospital Anxiety and Depression Scale Adult Carer Quality of Life Questionnaire	1) Prior to participant using ITG 2) After participant has used ITG for 4-6 weeks
Tertiary Objectives To evaluate the acceptability and usability of Information and Therapy guides for people with facial palsy and/or their friends and relatives	Participant satisfaction questionnaire	1) After participant has used ITG for 2-3 weeks 2) After participant has used ITG for 4-6 weeks

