9. STATISTICS AND ANALYSIS

9.1. Description of Statistical Methods

This study will follow a pre-post design and as such will use paired t-tests to observe whether a statistically significant change has occurred on each of the outcome measures, for each ITG. Descriptive statistics will also be provided (e.g. mean scores on each outcome measure at baseline).

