9.2. The Number of Participants

We aim to trial the ITGs over a period of two years (May 2019 – May 2021). This will lead to the predicted sample sizes of 140 participants (120 with facial palsy, 20 per each of the 6 guides; 20 friends and family). This target is based on there being approximately 3000 people who have access to the Facial Palsy UK website. Given that approximately 1/3 people with facial palsy experience a significant level of distress (5); we hope that our ITGs would be relevant to, and accessible by, around 1000 people. 140 is therefore a conservative estimate of the number of participants that we will be able to recruit. As this is an initial feasibility study, a power analysis was not conducted for the purposes of this study.

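### The Section 7.6 exclusion of withdrawn participants' data has no exception for 2-3 week satisfaction ratings already given, so acceptability and usability would be analysed only in people who stayed.

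*Combined protocol and SAP*

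**What the plan says.** The tertiary objective in Section 4 is "To evaluate the acceptability and usability of Information and Therapy guides for people with facial palsy and/or their friends and relatives". Its outcome, the participant satisfaction questionnaire, has two time points: "1) After participant has used ITG for 2-3 weeks 2) After participant has used ITG for 4-6 weeks". Section 7.5 describes the earlier one as part of the reminder contact: "They will also be sent a link to an online questionnaire, pertaining to their ratings of acceptability and usability of the ITG".

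Two passages govern people who leave:

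- Section 7.6 lists three reasons for discontinuation. The one on withdrawal of consent adds that "withdrawn participants will be replaced and their data will be excluded from analysis". The bullets on ineligibility and protocol deviation carry no such statement.
- Section 5, on the two weeks allowed for the final questionnaires, says: "If they do not complete the questionnaires in this window, they will be withdrawn from the study". It does not say whether these people's data are excluded or whether they are replaced.

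For analysis, Section 9.1 "will use paired t-tests to observe whether a statistically significant change has occurred on each of the outcome measures, for each ITG". Sections 9.1 and 9.3 define no analysis set and no missing-data rule for the satisfaction questionnaire. Section 9.2 plans "140 participants (120 with facial palsy, 20 per each of the 6 guides; 20 friends and family"), and states that "a power analysis was not conducted for the purposes of this study".

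**The concern.** For the wellbeing outcomes, excluding someone who left costs little: without a post score there is no pair to analyse. Acceptability is different. The 2-3 week rating exists, may be the only view of the guide that person ever gave, and is discarded under a rule that is not limited by outcome or by date of collection. Section 7.3 leaves participants free not to give a reason for withdrawing, so the rating may also be the only clue to why they left.

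The study calls itself a pilot and feasibility study and has no control group. Acceptability and usability are among the questions it is best placed to answer. Because leavers are replaced as well as excluded, a guide that loses many users can still reach its 20 without the loss showing in the analysed set. If the people who leave are those whom the guide suited least, the reported acceptability is too favourable.

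**Working it through.** **1. The plan's own figure.** 6 guides × 20 + 20 friends and family = 140, which reproduces Section 9.2. The documents give no withdrawal rate, satisfaction rate, alpha, power or effect size, so no stated figure measures the effect of the exclusion.

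**2. Whether the rule reaches the 2-3 week ratings.** The form is due at 2-3 weeks (Sections 4, 5 and 7.5) and the final assessment at 4-6 weeks. There is thus an interval in which a person has rated the guide and can still withdraw. Section 7.6 excludes that person's data with no carve-out, and Section 9 does not restore it. For people who withdraw consent, the reading is direct. For those who miss the final window, it depends on whether the word withdrawn in Section 5 carries the same consequence as in Section 7.6, which the documents do not settle.

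**3. Size of the overstatement.** Assume that satisfaction is summarised as a proportion (no passage defines the summary). Let d be the proportion who leave, p_stay and p_leave the proportions satisfied.

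- All who started: (1 − d) × p_stay + d × p_leave
- Reported under the exclusion: p_stay
- Overstatement: d × (p_stay − p_leave)

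With assumed p_stay = 80% and p_leave = 40%:

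| d (assumed) | All who started | Reported | Overstatement |
|---|---|---|---|
| 2% | 79.2% | 80% | 0.8 points |
| 5% | 78% | 80% | 2 points |
| 10% | 76% | 80% | 4 points |
| 20% | 72% | 80% | 8 points |
| 40% | 64% | 80% | 16 points |

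For d of 10-40%, letting p_leave range from 60% down to 20% gives 0.10 × 20 = 2 points up to 0.40 × 60 = 24 points. If p_leave = p_stay, the overstatement is 0.

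**4. If some leavers never returned a form.** The table assumes that every leaver's view is known. Suppose instead that half the leavers and all the stayers returned the 2-3 week form. Satisfaction among returned forms is then [(1 − d) × 0.80 + 0.5d × 0.40] / [(1 − d) + 0.5d]:

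- d = 10%: 0.74 / 0.95 = 78%, so about 2 points
- d = 25%: 0.65 / 0.875 = 74%, so about 6 points
- d = 40%: 0.56 / 0.80 = 70%, so 10 points

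**5. Replacement.** If 20 per guide is the number remaining after replacement, those who start number 20 / (1 − d), rounded up: 23, 25, 29 and 34 at 10%, 20%, 30% and 40%. About 3 to 14 people per guide would then fall outside the analysis. This counts everyone who leaves, including those who gave no rating.

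**The case against.** The strongest reply is that the rule is narrow. It sits only in the withdrawal-of-consent bullet. Someone who dislikes or abandons a guide but stays in the study is not excluded by it, and excluding data after consent is withdrawn can be a deliberate ethical choice. The consent form and information sheet are not part of the document reviewed, so what participants were promised cannot be judged. This stands, and it is why retention should yield to a request for deletion. It does not remove the point, because nothing in Section 7.6 or in the description of consent in Section 7.3 says whether ratings already given are kept.

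Second, attrition of 10-40% may be far too high for active withdrawal of consent. At 2-5% the shift is 0.8-2 points, small beside a standard error of about 9 points for an 80% proportion in 20 people (√(0.8 × 0.2 / 20) = 0.089). This also stands. The higher rates become relevant mainly if Section 5 non-returners are covered.

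Third, a reader might infer that withdrawals will go unreported. The text does not support that: Section 7.6 excludes data from analysis and does not bar giving counts, and Section 5 says recruitment and completion will be monitored. What is missing is a commitment to report them per guide.

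Fourth, Section 9 names no specific analysis for the satisfaction questionnaire. That gap is arguably more basic, but filling it would not by itself undo the exclusion.

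**Conclusion.** The point holds as a selection problem for the tertiary objective. Followed as written, the plan drops 2-3 week ratings from people who withdraw consent, and may drop those of people who miss the final window; Sections 5 and 7.6 need to be reconciled on this.

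The size is unknown. On the assumed 80% and 40%, it is about 1-2 points at 2-5% withdrawal and 4-16 points at 10-40%, and less among returned forms if some leavers returned none.

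Two stronger readings are tempting and go beyond the documents. One is that acceptability will certainly be inflated, so that poor guides will look as good as the rest. That requires leavers to be less satisfied, which no passage establishes. The other is that leaving during a later guide erases ratings of guides already completed. Section 7.6 does not say so, and because Section 7.5 seeks consent afresh for each further guide, the exclusion could equally be read guide by guide.

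The wellbeing comparisons are not the target here. This should be corrected because the ratings are already in hand and keeping them is simple.

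**What to change.** - In Section 7.6, limit the exclusion to the pre-post wellbeing analysis, and state whether people withdrawn under Section 5 for missing the final window fall under the same rule.
- In Section 9.3, state that the tertiary objective uses every 2-3 week satisfaction form returned, including from people who later withdraw or do not return the final forms, unless they ask for deletion. Show those who stayed and those who left separately.
- Report per guide the numbers sent the guide, returning the 2-3 week form, returning the final form, withdrawn, and replaced. Count replacements in addition to the people they replace.
- Add a sentence to the information sheet and consent form on what happens to answers already given.

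No new data collection is needed: the questionnaires are already scheduled and Section 10.2 provides an ID log. The cost is an amendment to the protocol and consent wording, which may need ethics committee and HRA approval under Section 12.3. Reported acceptability may also come out lower.
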